Efficacy Analyses: The primary efficacy endpoint will be analyzed using a repeated measures analysis of covariance on percent change-from-baseline variable to compare the time profile between treatments where the visit will be the time factor; and the stratification factor PGA score, treatment group, and interaction term for treatment-by-visit will be the fixed effects and the baseline value will be the covariate. An unstructured variance-covariance matrix will be used. For categorical efficacy endpoints involving proportions of PGA (e.g. the proportion of subjects achieving at least a 2-grade reduction from baseline to clear (0) or almost clear (1) in PGA at Week 16), a Cochran Mantel Hansel test (CMH) controlling for PGA score at baseline will be performed.		
Safety Analyses: The safety analysis will include reported AEs and other safety information (i.e., clinical laboratory evaluations, vital signs, physical examination, and 12-lead ECG results). A summary of safety results will be presented for each treatment group.		
PK Analyses: ASN002 concentration data will be summarized based on nominal timepoints using descriptive statistics, such as mean, SD, CV%, median, minimum and maximum. Population PK analysis will be performed using nonlinear mixed-effects modeling approach with first-order conditional methods. This analysis may be combined with PK concentrations from other clinical trials in healthy and AD subjects as appropriate.		
PD Analyses: Biomarker levels will be compared to placebo adjusted change from baseline over time for each treatment group, and the parameters will be summarized by treatment group and overall using descriptive statistics.		

Name of Sponsor/Company: Asana BioSciences, LLC	Name of Investigational Product: ASN002	Name of Active Ingredient: ASN002
PK/PD Analyses: PK-efficacy, PK-safety and PK-biomarkers relationships will be explored using linear regression, loess plots, Hills functions, or logistic regression, as appropriate.		
Primary statistical analysis: Unblinded primary efficacy analyses will be performed after Week 16 is completed for all subjects. The CRO team and the sponsor will be unblinded after the database lock of Part A for the efficacy assessments, and a cleaning and monitoring of all safety data collected in Part A. The sites, investigators and subjects will remain blinded throughout the study.		

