4 STUDY DESIGN

4.1 Overall Design

This study will be performed at approximately 20-25 study centers located in the United States and Canada.

Approximately 105 subjects with moderate to severe CHE (as defined by a hand PGA 3 or 4 at Day 1) will be included in this randomized, double-blind, placebo-controlled, multicenter, Phase 2 study. Subjects will be men or women, 18 years of age or older, at the time of consent. Subjects with moderate CHE will be limited to 30% of total enrollment.

Each subject should read and sign an informed consent form prior to any screening procedures being performed. Subjects who fulfill all of the inclusion criteria and none of the exclusion criteria will be accepted into the study. After a screening period of no more than 30 days (from Day -30 to Day -1), eligible subjects will be randomized (1:1:1) on Day 1 to receive ASN002 at 40 mg or 80 mg, or placebo once daily for 16 weeks (Part A). Then, in Part B, subjects who were assigned to placebo in the first part of the study will receive the highest dose of ASN002 (i.e. 80 mg) for the rest of the treatment period (up to Week 32). The subjects who were assigned ASN002 in the first part of the study will continue on the same assigned treatment dose during the second part of the study (Week 16 to Week 32). The total treatment period of 32 weeks will be followed by a 4-week follow-up period. For scheduled study visits, subjects will come to the study centers on 13 occasions: screening; Day 1; Weeks 2, 4, 8, 12, 16, 18, 20, 24, 28 and 32; and Week 36 (follow-up visit)/early termination (ET).

Efficacy will be assessed using mTLSS, PGA, HECSI, pain VAS and Extent of Disease. In addition, a 6-grade PaGA scale will be used. Quality of life will be evaluated using DLQI. Impact on work productivity and activity will be studied using the WPAI-SHP questionnaire.

Safety will be assessed by collecting AEs, recording vital signs, performing physical examination and 12-lead ECG, and evaluating clinical laboratory tests.

Pre- and post-dose PK blood samples will be collected from all subjects on a sparse sampling schedule on Day 1 and Weeks 2, 4, 8, 12, 16, 20, 24, 28, and 32 (or ET visit, if applicable).

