9.3.2 Efficacy Analyses

The primary efficacy endpoint will be analyzed using a repeated measures analysis of covariance on percent change-from-baseline variable to compare the time profile between treatments where

the visit will be the time factor (up to Week 16); and the stratification factor PGA score, treatment group, and interaction term for treatment-by-visit will be the fixed effects and the baseline value will be the covariate. An unstructured variance-covariance matrix will be used. Additional interaction terms will also be included in supportive statistical models and will be detailed in the SAP.

A similar approach as for the primary endpoint will be done for all other continuous efficacy endpoints.

For categorical efficacy endpoints involving proportions of PGA (e.g. the proportion of subjects achieving at least a 2-grade reduction from baseline to clear (0) or almost clear (1) in PGA at week 16), a Cochran Mantel Hansel test (CMH) controlling for PGA at baseline will be performed.

Overall type I error control

For the primary endpoint of percent change-from-baseline in hand mTLSS at Week 16, a Holm's step-down procedure (1979)¹⁴ adjustment will be done to test the two comparisons of interest (40mg vs. Placebo and 80mg vs. Placebo).

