3.4 Randomization, Replacement, and Unblinding Procedures

Subjects will be randomized in a 1:1:1 ratio to one of the following treatment regimens:

- Part A: ASN002 40 mg (16-week treatment); Part B: ASN002 40 mg (16-week treatment)
- Part A: ASN002 80 mg (16-week treatment); Part B: ASN002 80 mg (16-week treatment)
- Part A: Placebo (16-week treatment); Part B: ASN002 80 mg (16-week treatment)

Subjects assigned to regimen starting with a placebo in Part A (first 16 weeks) of the study will receive the highest dose of ASN002 (i.e. 80 mg) for the rest of the treatment period (up to Week 32). Subjects who were assigned to ASN002 in the first part of the study will continue on the assigned treatment dose during the second part of the study up 32 weeks of treatment.

Randomization will occur prior to first dosing, at Day 1 visit. The randomization list will be generated using validated software. Randomization will be stratified for the biopsy collection and for the PGA score of '3' (moderate) or '4' (severe) per treatment group. The master randomization list will be kept secured until the study blind is broken. This list will be uploaded into an Interactive Web Response System (IWRS). The investigator or designee will be able to acquire a randomization number for eligible subjects by connecting to the IWRS

This study will be double-blinded. At all times, treatment and randomization information will be kept confidential and will not be released to, the contract research organization (CRO), or the sponsor's study team until database lock of Part A is completed and all safety data has been cleaned and monitored. Investigators, subjects and clinical staff will remain blinded throughout the study.

PPD	STATISTICAL ANALYSIS PLAN, Version Final 1.0
Protocol Number: ASN002AD-202 V6.0	Sponsor: Asana BioSciences, LLC

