3.5 Changes to the Analysis from the Protocol

Summary of physical examination will not be presented as specified in sections 8.4.2 and 8.4.3 of the protocol as results are not collected unless they appeared as Clinical significance, in which case they are entered as an AE.

Percent change from baseline in hand PGA and foot PGA at Weeks 4, 8, 12, 16, and 32 will not be present as specified in section 3 of the protocol.

PPD	STATISTICAL ANALYSIS PLAN, Version Final 1.0
Protocol Number: ASN002AD-202 V6.0	Sponsor: Asana BioSciences, LLC

Subgroup analysis by PGA strata at baseline (3 vs. 4) will be performed on the primary endpoint (percent change in mTLSS) and key secondary endpoint (proportion with reduction in PGA) as specified in sections 13.1 and 13.2.

Subgroup analysis by baseline description of CHE (hyperkeratotic, fingertip or pompholyx) will be performed on the primary endpoint (percent change in mTLSS) and key secondary endpoint (proportion with reduction in PGA) as specified in section 13.3 for exploratory purpose.

Validated Investigator Global Assessment (for subjects with AD only) will be analyzed as specified in Section 13.3 for exploratory purpose.

The pruritus score portion of the mTLSS will also be analyzed for exploratory purposes as described in Section 13.3.

All secondary efficacy endpoints will be up to Week 16 (Part A). All secondary efficacy endpoints data after week 16 (after the Placebo patients have crossed over to ASN002) will be considered exploratory efficacy endpoints and will be presented using descriptive statistics.

All exploratory efficacy endpoints specified in section 3 of the protocol, will be summarized by all visits with assessment scheduled from Weeks 4 to Week 32 as specified in section 13.3, instead at Weeks 4, 8, 12, 16, and 32.

In section 9.3.2 of the protocol, Holm's step-down procedure adjustment was proposed to adjust for the two comparisons of interest (40mg vs. Placebo and 80mg vs. Placebo). It is well known that the Hochberg method is optimal than Holm's adjustment. Therefore, Hochberg adjustment will be used for the multiple dose/treatment comparisons. The decision for this changed was made before the unblinding. Since this change would not affect the conduct of the trial in any sense, no protocol amendment was made to account for this change.

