Fissures	0 = Absent 1 = Cracked skin affecting a small area of the hand 2 = Cracked skin affecting multiple areas of the hand and causing pain

PPD

STATISTICAL ANALYSIS PLAN, Version Final 1.0

Protocol Number: ASN002AD-202 V6.0

Sponsor: Asana BioSciences, LLC

	3 = One or more deep fissures and causing bleeding or severe pain
	0 = Absent
	1 = Occasional, slight discomfort a few times per day
Pruritus/pain	2 = Intermittent, causing discomfort frequently during the day
	3 = Persistent or interfering with sleep
^a 0 = absent; 1 = mild; 2 = moderate; 3 = severe.	

Descriptive statistics on hand mTLSS value will be presented by visit for each treatment group. Change from baseline and percentage change from baseline will be also summarized.

Primary Endpoint Analysis

Unblinded primary efficacy analyses will be performed after Week 16 is completed for all subjects. The CRO team and the sponsor will be unblinded after the database lock of Part A for the efficacy assessments, and a cleaning and monitoring of all safety data collected in Part A. The sites, investigators and subjects will remain blinded throughout the study. The primary efficacy analysis will be done using the mITT population and the PP population will be used as a supportive analysis.

A mixed effect model for repeated measures (MMRM) will be used to model the percent change from baseline in hand mTLSS. The model will include the stratification factor PGA score at baseline, if baseline PGA score is not highly correlates with baseline mTLSS score, treatment, visit and treatment-by-visit interaction as fixed effects and baseline hand mTLSS as a covariate. Primary comparison between Placebo and Treatment groups will be for Week 16 using contrasts. The unstructured (UN) variance-covariance matrix will initially be assumed. If the model does not converge using the UN covariance structure, the autoregressive (order 1) AR(1) structure will be used. If the AR(1) structure also does not converge, other covariance structures deemed appropriate to fit the data will be used. .

Distribution of residuals will be visually examined to determine whether substantial departures from normality and homogeneity of variance are apparent. If the data are inconsistent with the assumption of normality, either a normalizing transformation to the primary endpoint will be applied or a nonparametric analysis will be performed.

The same analysis will be performed on the per-protocol population.

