Dermatology Life Quality Index Questionnaire (DLQI) is a simple 10-question validated questionnaire that has been used in more than 40 different skin conditions. The DLQI is the most frequently used instrument in studies of randomized controlled trials in dermatology. The DLQI total score is defined as the sum of the 10 item scales, ranging from 0 to 30. If missing answers or mistakes, the following rules will be followed:

1. If one question is left unanswered this is scored 0 and the scores are summed and expressed as usual out of a maximum of 30.
2. If two or more questions are left unanswered the questionnaire is not scored.
3. If question 7 is answered 'yes' this is scored 3 even if in the same question one of the other boxes is ticked.
4. If question 7 is answered 'no' or 'not relevant' but then either 'a lot' or 'a little' is ticked this is then scored 2 or 1. If it is answered 'no', but the second half is left incomplete, the score will remain 0.

DLQI will be analyzed as follows:

- Change from baseline in hand Dermatology Life Quality Index (DLQI) at Weeks 2, 4, 8, 12, and 16.

Pain visual analog scale (VAS)

Pain intensity of the CHE will be recorded at the visits specified in Table 1 using a pain Visual Analog Scale (VAS). Pain intensity will be evaluated by asking subjects to place a line perpendicular to the VAS line at the point that represents their worst pain intensity over the last 24 hours.¹³ The pain VAS, represented in Figure 2 is a scale from 0 to 10, where 0 indicates no pain and 10 indicate the worst imaginable pain.¹³

Figure 2: Pain Visual Analog Scale

Pain VAS will be analyzed as follows:

PPD	STATISTICAL ANALYSIS PLAN, Version Final 1.0
Protocol Number: ASN002AD-202 V6.0	Sponsor: Asana BioSciences, LLC

- Change and percent change from baseline in pain visual analog scale (VAS) at Weeks 4, 8, 12 and 16.

Secondary Endpoint Analyses

The key secondary analysis will be based on the data from Part A with the exception of Time to PGA response analysis. MMRM as described for the primary efficacy analyses (Section 13.1) will be used to analyze the change and/or percent change in hand mTLSS, HECSI, DLQI and pain VAS for weeks 4, 8, 12 and 16 (Part A). Analyses will be based on the mITT population and supported by the PP population.

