For categorical efficacy endpoints involving proportions hand PGA, a Cochran Mantel Hansel test (CMH) stratified by baseline PGA will be presented by visit for Part A. Analyses will be based on the mITT population for all secondary parameters and supported by the PP population. Missing data at any post-baseline assessment will be imputed as a non-responder.

Actual values of PaGA will summarized descriptively using frequency and percentage.

Time to response relative to baseline (based on hand PGA) will be compared between treatments using the Kaplan Meier method. A subject will be considered censored if he has not met the event of interest at the end of the study or if the subject is lost to follow up at last observation. Those subjects will be censored at their last available hand PGA assessment.

Descriptive statistics will be presented for all secondary endpoints by visit and treatment group and sorted by Part A.

All endpoints relative Part B for the above assessments are considered exploratory only and will be summarized descriptively by initial treatment group and overall.

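### The SAP makes the PGA randomisation stratum optional in the primary model through an undefined correlation check, while the protocol includes it without condition and the change is not declared

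*SAP*

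**What the plan says.** - **Randomisation.** SAP 3.4, like protocol 6.3, makes PGA one of two stratification factors: "Randomization will be stratified for the biopsy collection and for the PGA score of '3' (moderate) or '4' (severe) per treatment group".
- **Protocol model.** Protocol 9.3.2 specifies a repeated-measures analysis of percent change in hand mTLSS in which "the stratification factor PGA score, treatment group, and interaction term for treatment-by-visit will be the fixed effects", with the baseline value as covariate. The synopsis (1.1) says the same. Neither attaches a condition to PGA.
- **SAP model.** SAP 13.1, Primary Endpoint Analysis: "The model will include the stratification factor PGA score at baseline, if baseline PGA score is not highly correlates with baseline mTLSS score". The terms for treatment, visit, their interaction and baseline mTLSS are unconditional. Only PGA depends on a check.
- **Definition of the check.** There is none. SAP 13.1 names no coefficient, cut-off, analysis set or timing. SAP 6.1 (Adjustments for Covariates) names only the baseline value.
- **Declared changes.** SAP 3.5 reports one departure from the same protocol section: "In section 9.3.2 of the protocol, Holm's step-down procedure adjustment was proposed to adjust for the two comparisons of interest", now replaced by Hochberg, with a note that this was decided before unblinding. The conditional PGA term is not listed.
- **Secondary endpoints.** SAP 13.2 reuses the model for mTLSS, the HECSI, the DLQI and the pain scale: "MMRM as described for the primary efficacy analyses (Section 13.1) will be used to analyze the change and/or percent change".

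**The concern.** The primary model should follow from the text alone. Here two analysts with the same data and different ideas of a high correlation would fit different models, and one of those is not the protocol's model. A reader who relies on SAP 3.5 to learn what changed would not find out.

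The likely motive is understandable. PGA and mTLSS rate the same seven signs and symptoms, so they overlap. But collinearity between two baseline covariates widens the standard errors of those covariates' own coefficients. It neither biases nor materially widens the randomised treatment contrast, which is the only quantity tested. At stake are a little power, if a prognostic stratum is dropped, and the pre-specification of the primary analysis.

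**Working it through.** **1. The plan's own figure, which is not in dispute.** Inputs from SAP 5.1 and protocol 9.1: SD 39, differences from placebo of 25 and 35 points, 25 per group, two-sided alpha 0.05, general F test. With group means 0, 25 and 35 (mean 20), the sum of squared deviations is 400 + 25 + 225 = 650. The noncentrality is 25 x 650 / 39^2 = 10.68. On 2 and 72 degrees of freedom the power is 82.5%, and 24 per group is the smallest size that reaches 80%. So 25 per group is reproduced. This calculation has no covariates and stays the same whichever model is used.

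**2. Can the reading of *highly* decide the model?** Simulation: 75 subjects, 21 of them moderate, 5,000 runs per setting. The true correlations are assumptions. Share of trials in which PGA would be dropped:

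| True correlation | cut-off 0.4 | 0.5 | 0.6 | 0.7 |
|---|---|---|---|---|
| 0.5 | 89% | 53% | 11% | under 1% |
| 0.6 | over 99% | 93% | 54% | 6% |

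The choice of cut-off can take the answer from almost always dropped to almost never dropped.

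**3. How high can the correlation be?** Protocol 4.1: "Subjects with moderate CHE will be limited to 30% of total enrollment". For a binary stratum with proportion p cut from a normal score, the ceiling is phi(z_p) / sqrt(p(1-p)). At p = 0.30 this is 0.3477 / sqrt(0.21) = 0.759. At 0.25 it is 0.734 and at 0.20 it is 0.700.

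**4. What PGA adds once mTLSS is in the model.** Let r be the PGA-mTLSS correlation and ry the correlation of each with outcome (assumed equal and of the same sign). The share of the remaining variance that PGA explains is (2 ry^2/(1 + r) - ry^2) / (1 - ry^2).

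| ry | r = 0.70 | r = 0.759 |
|---|---|---|
| 0.2 | 0.0074 | 0.0057 |
| 0.3 | 0.0175 | 0.0136 |
| 0.4 | 0.0336 | 0.0261 |

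**5. Power cost, normal approximation.** SD 39 is taken as the SD after adjusting for mTLSS. The standard error without PGA is 39 x sqrt(2/25) = 11.03. Because randomisation balances PGA, the true standard error is 11.03 x sqrt(1 - share) under either model; the model without PGA simply fails to credit it. At share 0.0336 the true standard error is 10.84:
- PGA included: 25/10.84 - 1.96 = 0.346, power 63.5%.
- PGA omitted: (25 - 1.96 x 11.03)/10.84 = 0.312, power 62.2%.

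The loss is 1.3 points. At share 0.0057 the powers are 62.28% and 62.07%, a loss of 0.2. At a 35-point difference the losses are 0.6 (89.75% against 89.14%) and 0.1 (88.92% against 88.81%). The nominal 5% test with PGA omitted has size 4.62% to 4.93%.

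**6. Simulation that counts the degree of freedom.** Week 16 ANCOVA as a stand-in for the MMRM, 25 per arm, 22 of 75 moderate, 20,000 runs per setting, difference 25:

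| r, ry | PGA included | PGA omitted |
|---|---|---|
| 0.70, 0.2 | 0.603 | 0.605 |
| 0.70, 0.4 | 0.613 | 0.602 |
| 0.759, 0.2 | 0.607 | 0.609 |
| 0.759, 0.4 | 0.616 | 0.606 |

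The Monte Carlo standard error is about 0.0035 per cell. Null rejection is 0.048 to 0.053 with PGA and 0.048 to 0.051 without.

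**7. Cost of keeping a useless PGA term.** In the simulations of step 2, when PGA has no effect on outcome, the standard error of the 40 mg contrast changes by at most 0.04 (11.05 against 11.09). When PGA has a 20-point effect and r = 0.5, including it lowers the standard error from 10.97 to 10.76.

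**8. Do the two models disagree?** On significance of 40 mg against placebo, in 0.3 to 1.4% of null trials and 1.5 to 4.1% of trials under the planned effects. Type I error is 4.2 to 5.2% for either fixed model, and 4.8 to 5.7% if the smaller of the two p-values were taken (Monte Carlo standard error about 0.3 points).

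**The case against.** The other side has a fair case that this hardly matters, and several of its points stand.

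- **The default is still the protocol's model.** If *highly* is read as 0.8 or more, PGA would almost never be dropped, given the ceiling of about 0.76. That is true, but nothing in the SAP says so.
- **The protocol defers detail to the SAP.** Protocol 9.3.1 defers type I error control and missing-data handling, and 9.3.2 defers extra interaction terms in supportive models. Neither makes a stated main effect of the primary model optional.
- **The proportion tests are not a counter-example.** For these SAP 13.2 says "a Cochran Mantel Hansel test (CMH) stratified by baseline PGA will be presented by visit for Part A", with no condition. That test has no mTLSS covariate, so the redundancy cannot arise there. It shows that the stratum is otherwise kept, and no more.
- **Carry-over is partly inference.** For change in mTLSS the condition carries over directly. For HECSI, DLQI and pain VAS the covariate would presumably be each measure's own baseline, and it is unclear whether the check applies. That is one more ambiguity.
- **The range 0.70 to 0.76 presumes a strict reading.** At r = 0.5 and ry = 0.4 the share is 0.0635 and the loss at 25 points is 2.5 (64.9% against 62.4%).
- **Conservatism is barely visible.** The approximation shows it, but the simulation in step 6 does not.
- **Alpha.** The figures use 0.05, although Hochberg may test a comparison at 0.025. There the largest loss in step 5 becomes 1.5 points (52.5% against 51.0%).

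None of this supplies the missing definition or a reason to drop the stratum.

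**Conclusion.** The concern holds and is minor. The SAP leaves the primary model undetermined on a randomisation factor, departs from protocol 9.3.2 and does not declare it. The likely power cost of dropping PGA is about nil to 1.3 points at a 25-point difference if only a strong correlation triggers the drop, and about 2.5 points under the looser reading examined. When PGA is weakly prognostic, dropping it costs nothing.

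These sizes rest on assumed correlations, on SD 39 standing for the residual SD, and on a single-visit ANCOVA in place of the MMRM. The textual finding rests on none of them. Because the check can be made blinded on baseline data, no type I error inflation is shown. The covariance fallback and the transformation rule in the same SAP section are separate matters.

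**What to change.** In SAP 13.1, delete the condition so that baseline PGA (3 or 4) is always a fixed effect in the primary MMRM, as in protocol 9.3.2. State in SAP 13.2 that the secondary MMRMs also include PGA unconditionally. Present any model without PGA as a labelled sensitivity analysis.

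If the sponsor prefers to keep a rule, the minimum is to name the coefficient and cut-off, apply it to blinded data before the Part A lock, say whether it is applied once or for each endpoint, and list it in SAP 3.5. Deletion is simpler and gives up nothing material.

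The cost is SAP wording only. No new data are needed, and the sample size and the proportion tests are unchanged.

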3 STUDY DESIGN

3.1 Overall Design

This study will be performed at approximately 20-25 study centers located in the United States and Canada.

Approximately 105 subjects with moderate to severe CHE (as defined by a hand PGA = 3 or 4 at Day 1) will be included in this randomized, double-blind, placebo-controlled, multicenter, Phase 2 study. Subjects will be men or women, 18 years of age or older, at the time of consent. Subjects with moderate CHE will be limited to 30% of total enrollment.

Each subject should read and sign an informed consent form prior to any screening procedures being performed. Subjects who fulfill all of the inclusion criteria and none of the exclusion criteria will be accepted into the study. After a screening period of no more than 30 days (from Day -30

PPD	STATISTICAL ANALYSIS PLAN, Version Final 1.0
Protocol Number: ASN002AD-202 V6.0	Sponsor: Asana BioSciences, LLC

to Day -1), eligible subjects will be randomized (1:1:1) on Day 1 to receive ASN002 at 40 mg or 80 mg, or placebo once daily for 16 weeks (Part A). Randomization will be stratified for the biopsy collection and for the PGA score of '3' (moderate) or '4' (severe) per treatment group. Then, in Part B, subjects who were assigned to placebo in the first part of the study will receive the highest dose of ASN002 (i.e. 80 mg) for the rest of the treatment period (up to Week 32). The subjects who were assigned ASN002 in the first part of the study will continue on the same assigned treatment dose during the second part of the study (Week 16 to Week 32). The total treatment period of 32 weeks will be followed by a 4-week follow-up period. For scheduled study visits, subjects will come to the study centers on 13 occasions: screening; Day 1; Weeks 2, 4, 8, 12, 16, 18, 20, 24, 28 and 32 (end of treatment visit); and Week 36 (follow-up visit)/early termination (ET).

[figure not shown]
Efficacy will be assessed using mTLSS, PGA, HECSI, pain VAS and Extent of Disease. In addition, a 6-grade PaGA scale will be used. Quality of life will be evaluated using DLQI. Impact on work productivity and activity will be studied using the WPAI-SHP questionnaire.

Safety will be assessed by collecting AEs, recording vital signs, performing physical examination and 12-lead ECG, and evaluating clinical laboratory tests.

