Overall type 1 error control

PPD	STATISTICAL ANALYSIS PLAN, Version Final 1.0
Protocol Number: ASN002AD-202 V6.0	Sponsor: Asana BioSciences, LLC

For the primary endpoint of percent change-from-baseline in hand mTLSS at Week 16, a Hochberg step-up procedure adjustment will be done to test the two comparisons of interest (40mg vs. Placebo and 80mg vs. Placebo) as detailed in Section 6.5.

Sensitivity Analysis:

Additional sensitivity analyses will be performed for the primary endpoint - percent change from baseline in mTLSS using MMRM model described above and including all efficacy hand mTLSS data for these subjects (before and after the prohibited medication).

Subgroup Analysis:

Subgroup analysis by PGA strata will also be presented for the primary endpoint -percent change from baseline in mTLSS. MMRM model will be used with treatment, visit and treatment-by-visit interaction as fixed effects, and baseline hand mTLSS as a covariate and primary comparison will be performed at Week 16.

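### The only named fallback covariance, AR(1), assumes one variance for all visits; if it is used and the SD changes by visit, the Week 16 standard error is wrong

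*SAP*

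**What the plan says.** Protocol 9.3.2 names one structure and no alternative: "An unstructured variance-covariance matrix will be used". SAP 13.1 starts in the same place, "The unstructured (UN) variance-covariance matrix will initially be assumed", and then adds an ordered fallback: "If the model does not converge using the UN covariance structure, the autoregressive (order 1) AR(1) structure will be used". The last step is open: "If the AR(1) structure also does not converge, other covariance structures deemed appropriate to fit the data will be used". AR(1) is therefore the only fallback named, and anything else comes in only after AR(1) has also failed. The SAP does not call it heterogeneous and gives no robust variance.

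The same section has residuals inspected by eye for both normality and equal variance. The action that follows (a transformation or a nonparametric analysis) is tied to non-normality alone.

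The visits in the model are not settled. Both schedules of events place mTLSS at Weeks 2, 4, 8, 12 and 16 in Part A. Protocol 9.3.2 says "the visit will be the time factor (up to Week 16", which does not exclude Week 2. SAP 13.2 applies the same model "to analyze the change and/or percent change in hand mTLSS, HECSI, DLQI and pain VAS for weeks 4, 8, 12 and 16 (Part A", without Week 2.

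The PGA-stratum analysis in SAP 13.1 reuses the approach: "MMRM model will be used with treatment, visit and treatment-by-visit interaction as fixed effects, and baseline hand mTLSS as a covariate". It names no covariance structure of its own and presumably inherits the same sequence.

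**The concern.** The primary comparison is at Week 16, the last Part A visit. A structure with one variance estimates that variance from all visits together and uses it for the Week 16 contrast. If Week 16 is more variable than the average visit, the standard error is too small. If it is less variable, the standard error is too large.

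A rising SD is a realistic case. Percent change is zero for everyone at baseline by construction, so its spread starts at nothing and builds. The fallback would then give Week 16 intervals that are too narrow, and in the mITT primary analysis the two Hochberg-tested p-values would be too small. The only trigger for leaving AR(1) is that it does not converge, which is rare for a two-parameter structure, so in practice the sequence would end there.

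**Working it through.** **The plan's own figure.** Inputs from SAP 5.1: SD 39, differences from placebo of 25 and 35, two-sided alpha 5%, F test, 25 per group. Group means 0, 25, 35 average 20, and the squared deviations sum to 400 + 25 + 225 = 650. Noncentrality at n = 25 is 25 × 650 / 39² = 10.68, which gives 82.5% power (80.8% at n = 24). Dropout: 25/0.75 = 33.3 and 25/0.70 = 35.7, so up to 35 per group is consistent. The sample size reproduces. The 39 is a single SD common to the arms; no SD by visit is given anywhere.

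**Correct reference.** With 25 completers per group, the standard error of a Week 16 contrast is 39 × √(2/25) = 11.03.

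**Effect of AR(1).** With complete data and a saturated treatment-by-visit mean, the Week 16 estimate does not change. Only its standard error does, to s × √(2/n), where s is the single SD that AR(1) fits. So:

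- ratio = s / 39
- two-sided type I error = 2 × [1 − Φ(1.96 × ratio)]

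Assumptions: SD is 39 at Week 16 and linear in time from the Week 2 value; correlation is exchangeable at 0.65. A time-decay correlation gives the same ratios to two decimals. AR(1) is fitted by maximum likelihood in the large-sample limit.

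| SD at Weeks 2, 4, 8, 12, 16 (assumed) | Weeks 2-16: s, ratio, type I error | Weeks 4-16: s, ratio, type I error |
|---|---|---|
| 22, 24.4, 29.3, 34.1, 39 | 30.7, 0.79, 12% | 32.3, 0.83, 10.5% |
| 24, 26.1, 30.4, 34.7, 39 | 31.6, 0.81, 11% | 33.0, 0.85, 9.7% |
| 28, 29.6, 32.7, 35.9, 39 | 33.4, 0.86, 9% | 34.5, 0.88, 8.3% |
| 32, 33, 35, 37, 39 | 35.4, 0.91, 7.5% | 36.1, 0.93, 7.0% |
| 39 throughout | 39.0, 1.00, 5% | 39.0, 1.00, 5% |
| 48, 46.7, 44.1, 41.6, 39 | 43.9, 1.13, 2.7% | 43.0, 1.10, 3.1% |

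A hand check on the first row: the root mean square of the five SDs is √[(22² + 24.4² + 29.3² + 34.1² + 39²)/5] = 30.4, and 30.4/39 = 0.78, close to the fitted 0.79. At n = 25 the reported standard error would be 30.7 × √(2/25) = 8.7 instead of 11.03.

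**Spacing.** With constant SD, time-decay correlation and Week 2 in the model, AR(1) changes the Week 16 standard error by less than 1%. The equal-variance assumption drives the result. The spacing does not.

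**Dropout.** Random dropout of 27.5% moves the ratios little: for Weeks 4-16 with SD rising from 30 to 39, from 0.90 to between 0.89 and 0.91.

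**Both doses under Hochberg.** By simulation under the global null, ratios of 0.93 and 0.81 give a familywise error of about 7.0% and 12.7%, against 4.8% with correct standard errors.

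**How likely is the fallback?** An unstructured matrix has 5 × 6/2 = 15 parameters for five visits, or 4 × 5/2 = 10 for four, with about 105 subjects planned. In simulated fits with five visits, SD rising from 24 to 39 and 27.5% random dropout, it converged in 100 of 100 trials at n = 105. It also converged in 150 of 150 at n = 31, about the size of the PGA = 3 stratum (30% × 105 = 31.5). Those fits used an EM algorithm without the baseline covariate and not SAS, so they are indicative only.

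**The case against.** The strongest reply is that the plan is already orderly. It prespecifies the unstructured matrix first, leaves it only on non-convergence, and is unlikely to reach AR(1) with about 105 subjects. This stands for the mITT primary analysis. The simulated fits do not show failure as likely in the PGA = 3 stratum either.

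It can also be said that a rising SD is assumed. This stands too. The score cannot fall below 0, so percent change is bounded at −100%, and the spread could narrow as subjects clear. The table shows that AR(1) is then conservative.

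A reader might infer that AR(1) makes the Week 16 standard error too small in general, that the shorter gap between Weeks 2 and 4 adds to this, and that Hochberg-tested p-values are affected wherever the fallback is used. The documents support none of the three. They give no SD by visit; Week 2 may not be in the model and its spacing hardly matters; and Hochberg covers only the two primary comparisons. Under SAP 6.5 the secondary p-values are nominal, and the stratum analyses lie outside the Hochberg family.

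What the reply does not answer is that the only named fallback imposes equal variance, and the check that might reveal a problem leads to no action.

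**Conclusion.** The point holds conditionally. Two things must happen together: the unstructured fit fails, and the SD of percent change differs by visit. Under a linear rise from 22-32 to 39, the Week 16 standard error is then about 0.79-0.91 of the true one (0.83-0.93 without Week 2). Under constant SD there is no error, and under a fall from 48 to 39 the single-contrast type I error is about 3%. These are large-sample figures that rest on assumed SD profiles and correlations. Because the trigger is unlikely in the full mITT set, this is a low-priority improvement and not a threat to the planned primary analysis.

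**What to change.** Before Part A unblinding, change the fallback sentence in SAP 13.1 to: unstructured, then heterogeneous Toeplitz, then ARH(1), then CSH, in place of homogeneous AR(1). Each of these keeps a separate variance for Week 16, so the change protects whichever way the SD moves. State also which post-baseline visits enter the model, in particular whether Week 2 does.

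If a robust (sandwich) variance is added for structures other than unstructured, specify a small-sample correction, and do not use an uncorrected one in the PGA = 3 stratum. In simulation, an uncorrected sandwich gave a type I error of 7.8% at 10 per arm and 9.5% at 7 per arm with normal critical values (6.6% and 7.6% with t), no better than many of the AR(1) cases above.

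The cost is a sentence or two in the SAP and a few more covariance parameters than AR(1).
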